The intervention will follow a manualized CBGT treatment developed by Hunter & Smith, 2015 aimed to reduce problematic vasomotor symptoms, stress, problems with sleep and enhance well-being. The CBGT will occur weekly for 6 weeks. Each week the CBGT is for 90 minutes. The underlying premise of CBGT is to promote stress coping and emotional regulation. This in turn will improve physiological regulation. For instance, improved stress coping decreases anxiety and allows women the opportunity to regulate their emotions and behaviors, potentially resulting in less physiologic lability. In addition, there is evidence to suggest that mood and stress and vasomotor symptoms are related to problems with memory and concentration. Problems with vasomotor symptoms, mood, memory and stress impact quality of life (Hunter & Smith, 2015). These symptoms will be assessed on the pre and post intervention. It is uncertain if the outcomes will be significant, which is why the research is being conducted. Since we are measuring each construct (i.e., hot flashes, daily life interference, quality of life), we will be able to test these theories.

Specific Aims and Exploratory Hypothesis

A manualized cognitive behavior group therapy treatment for vasomotor symptoms developed by Hunter and Smith (2105) has been found to significantly reduce hot flashes and night sweats for well women and women with breast cancer. The vasomotor symptoms of the participants were natural, surgically induced or followed medical procedures. Although not diagnosed with bipolar disorder, major depressive disorder or anxiety disorders, CBGT also reduced depressive and anxiety symptoms in these populations. However, the feasibility and effectiveness of this manualized treatment has not been studied for women who meet DSM-V criteria for bipolar disorder or major depressive disorder, with or without an anxiety disorder. In addition, no studies were found comparing Black and White females where group CBT was used as an intervention to reduce problematic vasomotor symptoms, quality of life and decrease daily interference.

Specific Aims:

1. Evaluate the feasibility of a manualized Cognitive behavior group therapy treatment for vasomotor symptoms for Black and White females diagnosed with bipolar disorder or major depressive disorder, with or without an anxiety disorder.

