2. Evaluate the effectiveness of a manualized Cognitive behavior group therapy treatment for vasomotor symptoms for Black and White females diagnosed with bipolar disorder or major depressive disorder, with or without an anxiety disorder.
3. Describe the characteristics for Black and White females diagnosed with bipolar disorder or major depressive disorder, with or without an anxiety disorder on the Hot Flush Frequency and Problem Rating Scale (HFFPRS), Hot Flash Daily Interference Scale (HFRDIS), Hot Flash Belief Scale (HFBS), Menopause Representation Questionnaire (MRQ), Montgomery Asberg Depression Rating Scale (MADRS), Perceived Stress Scale-10 (PSS-10), Snaith-Hamilton Pleasure Scale (SHAPS), Young Mania Rating Scale (YMRS), Structured Interview for the Hamilton Anxiety Rating Scale (SIGH-A) and the Short-Form Couple Conflicts (CTS2S).
4. Describe the following descriptive characteristics for Black and White females diagnosed with bipolar disorder or major depressive disorder, with or without an anxiety disorder: race/ethnicity, age, marital status, socioeconomic status, smoking status, average weekly alcohol and caffeine consumption, education, BMI, menopause status (early, late perimenopause, early, late post-menopause) and dosages and number of weeks on SSRI's, SNRI's, gabapentin or clonidine.

This study will also explore which independent variables are significant predictors of change in problematic hot flashes and night sweats, hot flash daily interference (HFRDIS), and menopause quality of life (MRQ) for peri- and post-menopausal Black and White females diagnosed with DSM-V bipolar disorder or major depressive disorder, with or without an anxiety disorder from baseline to post-treatment (6 weeks of Cognitive Behavioral Group Therapy). Examining which variables significantly contributes to the outcome variables will help direct non-pharmacologic treatment interventions and inform relevant psychoeducation for this population.

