It is expected that CBGT will reduce problematic hot flashes and night sweats (as measured via the hot flash frequency and problem rating scale), reduce daily interference (as measured on the hot flash daily interference scale), and improve quality of life (as measured on the MRQ). It is expected that strong negative beliefs about hot flashes and night sweats will be associated with more vasomotor symptoms and strong positive beliefs about vasomotor symptoms will be associated with significantly fewer vasomotor symptoms. The beliefs about vasomotor symptoms will be measured on the HFBS.

Overall Design: This is a 6-week cross-cultural study to test efficacy of CGBT treatment for 60 menopausal participants with major depressive disorder or bipolar disorder, with or without an anxiety disorder. The intervention will be delivered in groups of 5 to 10 participants per group of both race/ethnicities in an outpatient setting during a 6-week time period. The participants will be assessed on the degree of hot flash problem rating, hot flash related daily interference, and menopause quality of life at screening, baseline, and post-treatment. These are the outcome variables. Participants will be assessed using the following predictor variables at the same time points: BMI, level of perceived stress (PSS-10), severity of depression (MADRS), severity of

anxiety (SIGH-A), Snaith-Hamilton Pleasure Scale (SHAPS), Young Mania Rating Scale (YMRS), and hot flash beliefs. Severity of couple's conflict will be assessed using the CTS2S.

In addition, at the end of the study intervention, a questionnaire will be given to the participants to illicit feedback about the interventions. The purpose is to collect qualitative feedback that may be useful in future studies.

All participants will be seen for screening and treatment at University Hospitals Cleveland Medical Center, Mood Disorders Program [name].

Target Subject Population

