Medication regimens to treat their DSM-V diagnoses will be encouraged to continue in order to determine if the CBGT accounted for any change in symptoms.

Exclusion Criteria.

1. Unwilling or unable to comply to study requirements.
2. Women diagnosed with schizophrenia, schizoaffective, borderline personality disorder, and/or active psychosis, as confirmed by MINI.
3. Diagnosed with active substance use disorder within past 12 months as confirmed on the MINI.
4. Women currently taking HT for Vasomotor Symptoms (VMS).
5. Participants experiencing acute mania as defined by a Young Mania Rating Scale (YMRS) score > 15
6. Serious suicidal risks judged by the investigator or having score equal or greater than 4 on MADRS item number 10 at screening or baseline.
7. Participants being treated with chemotherapy and/or tamoxifen.
8. Women who are not self-identifying as either African-American or Caucasian.

Study Specific Procedures

Screening: After Informed Consent is obtained, the participants will be evaluated by the MINI International Neuropsychiatric Interview (MINI) for DSM-V Axis I diagnoses. The participants must be evaluated by the following clinician rated measurements: Montgomery Asberg Depression Rating Scale (MADRS), the Structured Interview for the Hamilton Anxiety Rating Scale (SIGH-A), the Young Mania Rating Scale (YMRS) and the Perceived Stress Scale-10 (PSS-10). In addition, the subject will complete the Quick Inventory of Depression Symptomatology-Self Report (QIDS-SR16). The clinician will gather demographics, take BMI measurements and document menstrual cycle patterns based on interview guidelines from the North American Menopause Society (NAMS).

At the end of this visit, participants who continue to meet all inclusion criteria and no exclusion criteria will be seen for a baseline visit. All qualifying participants will be asked to record The Hot Flush Weekly Diary for one week prior to Baseline visit.

During the study period, research staff and the primary investigator will be available to answer questions or concerns.

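### Do the outcome scales need a screening assessment because the Overall Design paragraph mentions one?

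*Combined protocol and SAP*

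**What the plan says.** Under Study Design & Objectives, the Overall Design paragraph lists the three outcome variables and gives three occasions for them: "hot flash problem rating, hot flash related daily interference, and menopause quality of life at screening, baseline, and post-treatment". It continues: "Participants will be assessed using the following predictor variables at the same time points", and then names BMI, PSS-10, MADRS, SIGH-A, SHAPS, YMRS and hot flash beliefs (the HFBS).

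The operative sections differ for five of these ten measures. The Screening paragraph of Study Specific Procedures covers the MINI, MADRS, SIGH-A, YMRS, PSS-10, demographics, BMI and menstrual history. Its only other questionnaire is the QIDS: "In addition, the subject will complete the Quick Inventory of Depression Symptomatology-Self Report (QIDS-SR16". HFFPRS, HFRDIS, MRQ, HFBS and SHAPS first appear under Baseline and are repeated under End of Study. In Table 1 their rows are blank at Screening and marked only at TX(1) and TX(6).

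Elsewhere the document describes two occasions. The design rationale says "These symptoms will be assessed on the pre and post intervention", and the text after the Specific Aims looks at predictors of change "from baseline to post-treatment (6 weeks of Cognitive Behavioral Group Therapy)". Statistical Analysis compares baseline with post-treatment by a matched-pairs t-test.

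**The concern.** Overall Design is where a reader looks to learn when the outcomes are measured, and for every outcome it disagrees with the schedule that staff will follow. Read alone, it suggests two pre-treatment values per woman on each outcome scale; the schedule yields one. Screening values that are not collected cannot be recovered later.

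That seems to matter because there is no control group. The same paragraph opens with "This is a 6-week cross-cultural study to test efficacy of CGBT treatment", and the sentence on continuing medication gives its purpose as "in order to determine if the CBGT accounted for any change in symptoms". A second pre-treatment value would give some view of how the outcomes move without therapy. If the protocol intended that and the schedule dropped it, the study would lose its only such look at the three outcome scales.

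**Working it through.** **1. Measures named in Overall Design against the schedule.** The schedule column is taken from Table 1 and agrees with the Screening, Baseline and End of Study paragraphs.

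| Measure | Role | Overall Design | Schedule |
|---|---|---|---|
| HFFPRS | outcome | 3 occasions | baseline, TX(6) |
| HFRDIS | outcome | 3 | baseline, TX(6) |
| MRQ | outcome | 3 | baseline, TX(6) |
| SHAPS | predictor | 3 | baseline, TX(6) |
| HFBS | predictor | 3 | baseline, TX(6) |
| BMI (weight) | predictor | 3 | screening, baseline, TX(6) |
| PSS-10 | predictor | 3 | screening, baseline, TX(6) |
| MADRS | predictor | 3 | screening, baseline, TX(6) |
| SIGH-A | predictor | 3 | screening, baseline, TX(6) |
| YMRS | predictor | 3 | screening, baseline, TX(6) |

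Missing at screening: 3 of 3 outcomes and 2 of 7 predictors, so 5 of 10. CTS2S is left out because Overall Design gives it no time point. The table has not been garbled in extraction: the prose visit lists agree with it, and the neighbouring QIDS and PSS rows do carry a screening mark.

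**2. Which text is the outlier.** Three time points for the outcomes appear in one summary sentence. Two appear in the design rationale, the text after the aims, the visit lists, Table 1 and the analysis. The summary sentence is correct for half the measures it covers, which fits a phrase that was true of the clinician ratings, PSS-10 and BMI being stretched over the whole list.

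**3. Effect on the planned analysis.** The test variable is post-treatment minus baseline, so a screening value does not enter it. Sample size determination gives N = 60, 20% dropout, d = 0.5 and two-sided alpha 0.017.

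- Completers: 60 × 0.8 = 48.
- Noncentrality of the paired t: d√n = 0.5 × √48 = 3.46, on 47 degrees of freedom.
- Power at alpha 0.017: 83.4%, which reproduces the stated figure of at least 80%.
- Power at alpha 0.05, the level that Statistical Analysis sets for all tests without adjustment: 92.4%.

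Both figures are the same under either reading of the schedule.

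**4. What collecting the outcomes at screening would cost and give.** By the item counts under Study Assessments, the three outcome scales add 5 + 10 + 32 = 47 items. Screening already carries 16 (QIDS-SR16) + 10 (PSS-10, by its title) = 26 self-report items, so the total becomes 73. Women who then fail screening would complete them too.

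The return is one descriptive contrast, screening to baseline, with three weaknesses:

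- **Interval.** It is at least one week, for the diary, with no stated maximum, because a group starts only once five women are enrolled. Baseline to TX(6) is 5 weeks in Table 1 (week 0 to week 5). The two changes would not cover matching periods.
- **Mode.** The site statement reads "All participants will be seen for screening and treatment at" the medical center, whereas Baseline allows e-mail or telephone. Part of any difference could be mode.
- **Selection.** Entry requires at least one hot flash or night sweat a day and a MADRS score above 7. Change just after screening may partly be regression to the mean from that selection.

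Its size cannot be derived from the documents. No stated aim or analysis uses it.

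**The case for a change.** The best case for acting is that Overall Design states a commitment for every outcome, staff working from Table 1 will not meet it, and the data are then lost for good. In a single-arm study a second pre-treatment value is worth something, and 47 items at an existing visit is a modest price. The Hot Flush Weekly Diary is no full substitute: it records frequency and intensity in the week before the intervention, not problem rating, interference or MRQ.

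Part of this stands. The texts do disagree, and on those three scales untreated change will not be observed. But the weakness comes from having no comparison group, and a screening value over an uncontrolled interval would not remove it. The study calls itself exploratory, and the phrase about CBGT accounting for change explains why medication is kept stable; it says nothing about assessment times. Pre-treatment information is also not absent: the diary covers the week before the intervention, and MADRS, SIGH-A, YMRS, PSS-10 and QIDS are taken at both screening and baseline. Changing a consistent schedule to fit one stray sentence would be a design preference and would not correct an error.

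**Conclusion.** The inconsistency is real and clerical. Overall Design overstates the number of assessments for 5 of 10 measures, including all 3 outcomes. Staff have consistent visit lists and a matching table, and an analyst has an unambiguous contrast from baseline to post-treatment. The effect on the planned test is nil: power at 48 completers and d = 0.5 is 92.4% at 0.05, or 83.4% at the sample-size level of 0.017, under either reading.

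Tidying the sentence would change nothing that the trial does or concludes. Adding the scales at screening is a trade-off whose return no aim or analysis needs. How far a before-after change can be credited to the therapy is a question for the single-arm design, whatever is done about this sentence.

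This conclusion assumes that the visit lists and Table 1 are what sites follow, and that no analysis beyond those described relies on a screening value of HFFPRS, HFRDIS, MRQ, SHAPS or HFBS. The documents mention none.

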Baseline: All participants will be asked to complete the following self-rated assessments: Hot Flush Frequency and Problem Rating Scale (HFFPRS), Hot Flash Belief Scale (HFBS), Menopause Representation Questionnaire (MRQ), Hot Flash Related Daily Interference Scale (HFRDIS), Snaith-Hamilton Pleasure Scale (SHAPS), Quick Inventory of Depression Symptomatology-Self Report (QIDS-SR16) and the Short-Form Couple Conflicts (CTS2S) scale within 2 days before or the day of the first group session. All participants will also be evaluated by clinician-rated assessments using the Montgomery Asberg Depression Rating Scale (MADRS), the Structured Interview for the Hamilton Anxiety Rating Scale (SIGH-A), the Young Mania Rating Scale (YMRS), and the Perceived Stress Scale-10 (PSS-10) within 2 days

before or the day of the first group session. All participants will be weighed at baseline. Baseline assessments can be done in person, via e-mail, or over the phone.

Study Interventions (week 0 through week 5):

Cognitive-Behavioral Group Therapy (CBGT)

The CBGT intervention will be delivered in groups of 5 to 10 participants including both African American and Caucasian females in an outpatient setting during a 6-week time period.

Treatment groups will start their first session when a minimum of 5 participants are conveniently enrolled, and each session will last for 1.5 hours. CBGT intervention will be facilitated by the primary investigator. The principal investigator will have periodic conference calls with Dr.

[name] to review the conduct of the group sessions and to discuss any concerns/questions.

[name] originally created the manual, and her role is serving as an advisor of this study.

Hunter & Smith's manual was developed from research studies on well-women and women with breast cancer (Alder et al., 2006; Mann et al., 2012). Permission has been given by [name] to use this manual in the proposed study. The six sessions are outlined in the manual entitled: *Managing Hot Flushes with Group Cognitive Behaviour Therapy: An Evidenced-Based Treatment Manual for Health Care Professionals* (Hunter & Smith, 2015) as follows:

Session 1: Psycho-education and the cognitive behavioural model

Session 2: Stress management, improving wellbeing and identifying precipitants

Session 3: Managing hot flushes using a cognitive behavioural approach

Session 4: Managing night sweats and improving sleep (part one)

Session 5: Managing night sweats and improving sleep (part two)

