Concomitant medication(s): we will collect concomitant medication information on all medications a participant is taking at the time of screening and within the 90 days prior to screening. Participants will be asked if there have been any changes to medications at each study session.

Participant-rated

Quick Inventory of Depression Symptomatology-Self Report (QIDS-SR16): This 16-item scale will be used to measure depression severity. This self-reported questionnaire was developed based on the DSM-V diagnostic criteria for a major depressive disorder episode.

The Hot Flush Weekly Diary: This objectively measures the frequency and intensity of daily hot flashes and night sweats. It is used one week prior to starting the intervention to gather baseline data and then weekly during the CGBT sessions.

The Menopause Representation Questionnaire (MRQ): This is a 32-item scale developed by Hunter & O’Dea (2001) to assess the cognitive appraisal of menopause. The questionnaire was derived from self-regulation theory. The MRQ consists of 2 sections (identity and beliefs subscales). The identity scale measures symptoms that are attributed to menopause. The greater the symptom attribution to menopause the greater menopause was viewed as having a bigger impact on their life. The items on the identity scale are scored from 0-2, with *Yes= 2, Uncertain= 1 and No=0*. Summation of scores range from 0-40. The beliefs scales consists of 6 subscales, measuring positive and negative consequences of menopause, time frame and the coping/control scale, which measures feelings of control over menopause symptoms. The belief scale items are scored on a Likert scale- *Strongly Agree (5) to Strongly Disagree (1)*. Negative impact (1,4,6,10,12), relief/new phase (2,11,13) and control/coping (5,8,14,17) are used in the current study as they have higher reliability (personal communication with the author).

Hot Flush Frequency and Problem Rating Scale (HFFPRS): This is a 5-item rating scale assessing hot flush frequency and how much those hot flushes cause problems, distress or interferes with daily routine.

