The Structured Interview for the Hamilton Anxiety Rating Scale (SIGH-A): This is a 14-item clinician-rated measure designed to assess the severity of anxiety.

Young Mania Rating Scale (YMRS): This is an 11-item clinician rated instrument designed to quantify severity of participant’s current symptoms of mania

BMI: A standard BMI calculator will be utilized for height and weight.

Table 1: Study Procedures Schedule

	Screening	TX(1) Baseline	TX(2)	TX(3)	TX(4)	TX(5)	TX(6) End of Intervention
Weeks		0	1	2	3	4	5
Visit	1	2	3	4	5	6	7
Intervention		X	X	X	X	X	X
Clinician Rated Assessments							
Demographics and Height	X						
Weight	X	X					X
Tracking and Documentation of Menstrual Cycles	X						
MINI	X						
MADRS	X	X					X
YMRS	X	X					X
SIGH-A	X	X					X
Concomitant Medications	X	X	X	X	X	X	X
Patient Rated Assessment							
QIDS	X	X	X	X	X	X	X

PSS	X	X					X
The Hot Flush Weekly Diary		X	X	X	X	X	X
HFFPRS		X					X
MRQ		X					X
HFBS		X					X
HFRDIS		X					X
SHAPS		X					X
CTS2S		X					X
Managing Menopausal Symptoms: Evaluation of Groups							X

Medication regimens to treat their DSM-V diagnoses will be encouraged to continue in order to determine if the CBGT accounted for any change in symptoms. Changes to medications during study participation will not be permitted. All concomitant medications taken during the study will be documented, including information on the indication, dosing, and dates of administration.

Efficacy & Data Analysis

Statistical Analysis:

Descriptive statistics will be used to describe demographic and clinical variables. This includes means and standard deviations for continuous variables and number and percentages for categorical variables. Difference in outcome measures from baseline to post-treatment will be determined by a matched-pairs *t*-test. Regression analysis will be used to assess the significance of the covariates on the differences of the 3 outcome variables. The significance of the race covariate in the regression models will be of special interest to the study. Statistical significance will be based on a Type I error rate of 0.05 for all statistical tests (two-tailed). Since this is an exploratory study no adjustment will be made for multiple comparisons.

Sample size determination.

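### A single-arm pre/post t-test cannot show that CBGT works or caused the change, as the protocol says it will; the baseline window should also close before session 1

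*Combined protocol and SAP*

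**What the plan says.** **Design and test.** Under Participants, all sixty women are to take part in the CBGT; no control or comparison condition appears anywhere. The Statistical Analysis says "Difference in outcome measures from baseline to post-treatment will be determined by a matched-pairs" t-test, adds regression of the three outcome differences on covariates, and sets the threshold: "Statistical significance will be based on a Type I error rate of 0.05 for all statistical tests (two-tailed").

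**Claims attached to it.** The Overall Design paragraph describes the study as a test of the efficacy of CBGT. The sentence after the inclusion criteria, repeated below Table 1, says that continuing psychiatric medication serves to establish whether CBGT was responsible for symptom change. Specific Aim 2 speaks of evaluating effectiveness.

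**Baseline timing.** The Baseline section places the self-rated and clinician-rated scales "within 2 days before or the day of the first group session" and adds: "Baseline assessments can be done in person, via e-mail, or over the phone". Table 1 puts baseline and the first treatment session in one column (week 0, visit 2). Elsewhere a pre-treatment baseline is plainly meant. Study Design & Objectives says "These symptoms will be assessed on the pre and post intervention". The Screening section has women "asked to record The Hot Flush Weekly Diary for one week prior to Baseline visit". The diary entry under Study Assessments says "It is used one week prior to starting the intervention to gather baseline data and then weekly during the CGBT sessions". Exclusion criterion 6 also relies on baseline data: it includes a "score equal or greater than 4 on MADRS item number 10 at screening or baseline".

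**The concern.** A matched-pairs t-test tests whether mean change is zero. It does not test why the change occurred. With every woman treated, the change combines any effect of CBGT with whatever would have happened over the same weeks: the natural course of vasomotor symptoms, expectation and group attention, and some regression to the mean, since women enter on current symptoms (at least one hot flash or night sweat per day, MADRS above 7). Holding medication constant deals with medication only. If the protocol's wording carries over to the report, a significant result will be read as evidence of efficacy that the design cannot provide.

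The baseline gap is a separate and smaller matter. Session 1 delivers active content (psycho-education and the cognitive behavioural model). A questionnaire returned by e-mail that evening meets the window as written but is no longer a pre-treatment value. The baseline part of exclusion criterion 6 could likewise fall after therapy has begun, although the screening check and the investigator's judgement remain.

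**Working it through.** **1. The plan's own figure.** Inputs from Sample size determination: N = 60, dropout 20%, d = 0.5 for the baseline-to-post difference, two-sided alpha 0.017.

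- Completers: n = 60 × 0.8 = 48, so df = 47.
- Paired t-test power = P(|T| > t_crit), where T is noncentral t with noncentrality d√n.
- d√n = 0.5 × √48 = 3.464; t_crit at alpha 0.017 is 2.475; power = 83.4%.

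The stated power of at least 80% is reproduced. At the analysis alpha of 0.05 (t_crit = 2.012) power is 92.4%. The sample size is sound for detecting a change.

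**2. What the same test does if CBGT has no effect but symptoms drift.** The formula is unchanged, with d replaced by an assumed non-specific improvement δ in SD of change. The documents give no value for δ, so a range is shown.

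| δ (assumed) | δ√48 | P(significant), alpha 0.05 | P(significant), alpha 0.017 |
|---|---|---|---|
| 0.1 | 0.693 | 10% | 4% |
| 0.2 | 1.386 | 27% | 15% |
| 0.3 | 2.078 | 53% | 36% |

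These results are not false positives for change, because the change is real. They are false only if read as an effect of CBGT. A stricter alpha lowers the percentages but does not alter what the test can show.

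**3. Could the planned N support a controlled test instead?** Splitting 60 into two arms leaves 24 completers each. With an assumed between-arm d of 0.5 (normal approximation), power is 41% at alpha 0.05 and 26% at 0.017. The planned N suits a pre/post estimate, not a controlled efficacy test of that size.

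**4. Baseline timing, sections side by side.**

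- End of Study states the order: data are collected after the last session ends or within two days of it.
- The diary is placed before the intervention, in Screening and in Study Assessments. It is not one of the three outcome variables.
- For the HFFPRS, HFRDIS and MRQ at baseline, the window includes the whole day of session 1, by any of three modes, with no order stated.

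No document gives the share of effect reached after one session or the proportion of women likely to be assessed late, so the bias cannot be sized. Its direction is also open: early benefit would shrink the measured change, while greater awareness of symptoms after session 1 could enlarge it.

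**5. Screening mismatch.** Overall Design lists the three outcomes at screening, baseline and post-treatment, and places the predictors, including SHAPS and hot flash beliefs, at the same time points. The Screening, Baseline and End of Study sections and Table 1 schedule the HFFPRS, HFRDIS, MRQ, SHAPS and HFBS at baseline and end of study only. The t-test and the sample size both use baseline-to-post change, so no planned result depends on the difference.

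**The case against.** **On the claims.** The study calls itself exploratory in its objectives and its Statistical Analysis, feasibility is Aim 1, and the protocol admits that it is uncertain whether outcomes will be significant. The statistical text itself speaks only of a difference from baseline to post-treatment. The Introduction gives the reason for stable medication more modestly: to make it less likely that a reduction is due to drugs. Regression to the mean may be limited, because the entry threshold is low and none of the three outcome scales is used for selection. The drift table would apply to any single-arm study of 48.

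Much of this is fair, and it is why the remedy is one of wording. It does not remove the problem. In the Statistical Analysis, the word exploratory justifies making no multiplicity adjustment; it does not limit causal conclusions. The modest medication rationale does not cancel the two statements that go further. No section says that the missing comparator limits attribution. Weak regression to the mean still leaves natural course and expectation.

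**On the baseline.** A reader might infer that the plan intends, or permits by design, measurement after session 1. The documents do not support that: the sections quoted above show that a pre-intervention baseline is meant, and the shared Table 1 column says nothing about order. What stands is a missing rule. A reader might also infer that late baselines would understate the effect and cost a calculable amount of power. Nothing in the documents fixes the direction or the size, and any figure would depend entirely on an assumed gain from session 1.

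**Conclusion.** The claims of efficacy and attribution are wrong as written for this design. A significant baseline-to-post change would show that women changed over six sessions of CBGT, not that CBGT caused it. The 10%, 27% and 53% figures illustrate how readily modest drift would give a significant test at 0.05. They rest on 48 completers, no therapy effect and assumed drift of 0.1 to 0.3 SD of change; they are not estimates for this population.

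It would go too far to conclude that the t-test is invalid, that the sample size is wrong, or that a control arm must be added. The test suits a question about change, and the stated power is reproduced.

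The baseline window is a real but secondary gap, of unknown size and uncertain direction. The screening mismatch is clerical. Overall this should be changed, at little cost.

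**What to change.** 1. **Claims.** In Overall Design, and in the medication statements after the inclusion criteria and below Table 1, replace the wording on efficacy and attribution with wording on change over the course of CBGT. Read Aim 2 with the same limit. Add a sentence to the Statistical Analysis that a significant pre/post change cannot be attributed to CBGT alone, because natural course, expectation and regression to the mean are not controlled. Cost: a more modest claim.
2. **Baseline.** State in the Baseline section, and in a note to Table 1, that baseline outcome assessments are completed before session 1 starts, whatever the mode. Record the date and time of completion. If any are late, report how many and repeat the t-test without them. Reconcile the Baseline section with exclusion criterion 6 on when the baseline eligibility check takes place. Cost: some staff time before the session for groups of 5 to 10 women, eased by the existing two-day window and remote options.
3. **Schedule wording.** Correct Overall Design so that the HFFPRS, HFRDIS, MRQ, SHAPS and HFBS appear at baseline and post-treatment only. Do not simply delete screening from the sentence, because weight, MADRS, SIGH-A, YMRS and PSS-10 are scheduled then; list the two sets separately. Cost: an edit.

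None of this changes the sample size, the alpha or the planned test.
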